CONFIDENTIAL

CLINICAL TRIAL PROTOCOL

A randomised, double-blind, placebo-controlled phase 2 trial of FOL-005 to investigate efficacy on hair growth on scalp skin in healthy volunteers

Trial code:	FCS-002	Trial development phase:	Phase 2
EudraCT number:	2017-003809-17	Investigational medicinal product:	FOL-005 solution for injection
Version:	1.0	Date:	07 November 2017

Coordinating Investigator:	[name]. [name]
Sponsor Signatory:	[name], CEO

This document contains confidential information. The contents may not be used, divulged or published without prior written consent of Follicum AB. This information cannot be used for any other purpose than the conduct and evaluation of the clinical investigation by the investigator(s), the regulatory authorities and members of the ethics committees

Name of Company:	Individual trial table	(For national authority use only)
Name of Active Ingredient:		
 Name of Investigational Products: FOL-005 Solution for injection Placebo solution for injection 		Trial under an IND: No
Title of trial: A randomised, double-blind, pla on hair growth on scalp skin in h	cebo-controlled phase 2 tria nealthy volunteers	l of FOL-005 to investigate efficacy

Planned trial period:	Phase of development:
January 2018 – June 2018	Phase 2

Objectives:

Primary objective:

The primary objective of this trial is to evaluate the efficacy of FOL-005 on scalp hair density in healthy male subjects when applied intradermally three times weekly for 12 weeks.

Secondary objectives are:

The secondary objective of this trial is to evaluate the efficacy of FOL-005 on scalp hair density in healthy male subjects when applied intradermally three times a week for 8 weeks and to evaluate the safety and tolerability of 12 weeks of treatment with FOL-005 in healthy male subjects.

Methodology:

The trial is a multicentre, randomised, double-blind, placebo controlled phase 2 trial

60 healthy bald male subjects diagnosed with androgenic alopecia (Norwood/Hamilton grade 3V to 4/4a), who are between 18 and 55 years old and provide written informed consent will be eligible for inclusion.

The trial period will consist of a screening period of up to 1 week followed by 12 weeks of dosing, three times per week. Each subject will receive two doses of the four trial treatment doses (0.00625, 0.025, 0.050, and $0.100 \mu g$ respectively) and the placebo dose. On each volunteer, two treatment areas will be selected on the head and the two selected doses will be allocated to the respective treatment areas according to the randomisation scheme. The treatment areas will be selected on the border between the bald surface and the surface with hair.

The subjects will be screened for eligibility at the screening visit where a physical examination and assessment of vital signs will be performed. Blood samples for safety and laboratory assessment will be taken. The subjects will return to the clinic for the inclusion visit (visit 1, day 1) 3 to 21 days later. If the subject is eligible for inclusion, the 2 treatment areas will be shaved and the centre of each treatment area where the trial treatments will be applied will be marked with a tattooed dot.

At visit 2, day 5, the first trial treatment application will be performed after TrichoScan imaging of the treatment areas. Subjects will then return to the clinic for treatment application three times per week with at least one day in between.

All subjects who have received at least one dose of trial drug will go through the procedures for safety and efficacy assessments at last visit (EOT, visit 38).

All adverse events will be followed until resolved or stabilised. Procedures for removal of subjects from therapy or assessments are described in Section 8.7.

Number of subjects:

A total of 60 healthy male subjects will be included.

Each subject will be treated at two sites. Each site will be treated with different treatments.

Thus, a total of 120 treatment areas will be available for treatment on the 60 subjects

Inclusion criteria:

The subjects must meet all of the following criteria to be eligible to enter the trial:

- 1. Healthy male, aged 18-55 years
- 2. Androgenetic alopecia (AGA)) Norwood/Hamilton grade 3V to 4/4a [1]
- 3. Caucasian, skin type I IV according to Fitzpatrick's classification [2]
- 4. Willing to have treatment areas shaved for TrichoScan® measurement marked with small semi-permanent dot tattoos
- 5. Willing and able to comply with scheduled visits
- 6. Willing to maintain the same hygiene products and skin cleansing habits during the trial period.
- 7. Willing to continue to use the currently used shampoo throughout the course of the trial.

8. Following verbal and written information about the trial, the subject has to provide signed and dated informed consent before any trial related activity is carried out.

Exclusion criteria:

Subjects meeting any of the following criteria will not be permitted to enter the trial:

- 1. Damaged skin in or around test sites including sunburn, uneven skin tones, tattoos, scars or other disfiguration of the test sites risking interfering with investigational evaluations
- 2. Any dermatological disorders of the scalp which might interfere with the application of IMP or examination method, such as fungal or bacterial infections, seborrheic dermatitis, psoriasis, eczema, folliculitis or scalp atrophy
- 3. Any skin pathology (e.g. scar, nevus) or general condition (e.g. uncontrolled thyroid diseases) that in the investigator's opinion can interfere with the evaluation of the treatment areas or requires topical or systemic therapy
- 4. History of active hair loss due to alopecia areata, scarring alopecia, diffuse telogen effluvium or conditions other than androgenetic alopecia
- 5. Use of or planned use of any shampoo with expected medicinal effect on the scalp (e.g. but not limited to antifungal or anti-dandruff shampoo, shampoo containing urea, caffeine or acetylsalicylic acid, etc.) during the course of the trial
- 6. Known or suspected allergy or sensitisation to any of the IPs or excipients
- 7. Immunological disorders such as alopecia areata, and systemic lupus erythematosus and other systemic known autoimmune disorders
- 8. Diabetes mellitus
- 9. Topical treatments for hair growth (minoxidil, anti-androgens or other agents known to affect hair growth) in the last 6 months
- 10. Topical scalp over-the-counter (OTC) or cosmetic treatments including shampoos known to affect hair growth in the last 4 weeks
- 11. Topical treatments of the scalp including corticosteroids, tacrolimus, retinoids in the last 2 months or other treatments that may affect hair growth
- 12. Platelet rich plasma (PRP) treatment on scalp during the last 12 months
- 13. Systemic therapy using retinoids, cyclosporine within the last 3 months
- 14. Systemic treatment with beta blockers or corticosteroids, scalp procedures e.g. surgery, laser, light, micro-needling within the last 6 months
- 15. Finasterid (e.g. Propecia®) or Dutasteride intake in the last 12 months, or any systemic hair therapy medication in the last 12 months
- 16. Other systemic therapy which in the opinion of the investigator might affect hair growth
- 17. Known needle fear or loss of consciousness while having blood sample taken or receiving injections
- 18. History of any acute (e.g. acute infections) or chronic illness (e.g. psoriasis, atopic dermatitis, porphyria) or known skin cancer that in the opinion of the investigators might confound the results of the trial
- 19. History or clinical signs of keloids or hypertrophic scars

- 21. Elevated values for vital signs:
 - blood pressure: systolic above 160 mmHg, diastolic above 95 mmHg
 - heart rate: above 100 beats/min.
- 22. Current or within 2 weeks prior to first dosing use of vasodilating drugs (e.g. Pentoxifyllin, nitroglycerine) or anticoagulating drugs (e.g. heparine, cumarines, new oral anticoagulants, regular intake of acetylsalicylic acid)
- 23. Current or within 3 months prior to first dosing use of anti-inflammatory medication (ibuprofen, paracetamol is permitted), corticosteroids (nose drops, eye drops and/or inhalers are permitted) or immunosuppressive drugs taken for more than 2 consecutive weeks
- 24. Current or within the last 6 months history of severe dietary or weight changes
- 25. Hair transplantation at any time
- 26. Known sensitization to cosmetic hair dyes or hypersensitivity to ingredients of the IMP or tattoo ink.
- 27. Planned or scheduled subject surgery or hospitalisation during the course of the trial
- 28. Any condition for which the investigator determines that the subject could be placed under undue risk.
- 29. Participation in any clinical trial within the last four weeks
- 30. Previously randomised in this trial
- 31. Subject is institutionalized because of legal or regulatory order
- 32. Close affiliation with the investigator (e.g. a close relative) or persons working at the trial site, or subject that is an employee of sponsor
- 33. In the opinion of the investigator unlikely to comply with the clinical trial protocol

Investigational products, dose and mode of administration:

The trial treatments will consist of three times per week application of:

- FOL-005 0.00625 µg solution, or
- FOL-005 0.025 µg, or
- FOL-005 0.050 µg, or
- FOL-005 0.100 µg, or
- FOL-005 placebo.

The treatment will be randomized to the 120 treatment areas in the ratio of: 5:5:5:5:4, i.e. 5 of each active treatment and 4 of placebo.

The investigational products will be administered as a local intradermal injection of 50 μl solution into the skin.

Treatment areas

Two mini-zones (circle of 1.5 cm diameter), located on 2 contra-lateral zones, the right and left sides of the frontal areas of the scalp. Areas should be located in a transitional area of hair loss. The middle of each treatment area will be identified by a dot micro-tattoo, to ensure that the same area is treated, documented and evaluated throughout the study.

Duration of treatment:

In total 12 weeks of dosing three times weekly

Assessments

Efficacy assessment:

• Hair growth parameters on treatment areas using TrichoScan® software at Baseline and weeks 8 and 12.

Safety

assessments:

- Adverse events
- Local tolerability
- Vital signs including supine systolic and diastolic blood pressure (mmHg), supine heart rate (beats per minute), body temperature
- Physical examination including general appearance, mouth and throat, ears (left and right), lungs, abdomen, neurological
- Blood and Urine sampling

Criteria for evaluation:

Efficacy variables:

- Čumulative hair thickness (mm/cm²)
- Hair thickness (µm/cm², mean median)
- Hair length (mm/cm²; mean, median)
- Total hair density (n/cm²)
- Terminal hair density (n/cm²)
- Vellus hair (<40µm thick) density (n/cm²)
- Total hair growth (µm/day/cm²)
- Hair growth (µm/day/cm², mean median)
- Anagen hair density (n/cm²)
- Telogen hair density (n/cm²)

Safety and tolerability variables:

- Any adverse events reported (including change in vital signs, physical examination and safety laboratory parameters)
- Any adverse drug reaction reported (including change in vital signs, physical examination and safety laboratory parameters)
- The reasons for withdrawal from the study
- Local tolerability; Erythema, Haematoma, dyspigmentation, induration and pain/discomfort will be assessed on a 4-graded scale (none, mild, moderate and severe)

Endpoints:

Primary endpoint:

Change from baseline of total hair density (No. of hairs per cm²) on the scalp after 12 weeks of treatment

Secondary endpoints are:

Change from baseline of total hair density (No. of hairs per cm²) on the scalp after 8 weeks of treatment

Change from baseline of hair growth parameters after 8 and after 12 weeks of treatment:

- Cumulative hair thickness (mm/cm²)
- Hair thickness (µm/cm², mean median)
- Hair length (mm/cm²; mean, median)
- Terminal hair density (n/cm²)
- Vellus hair (<40µm thick) density (n/cm²)
- Total hair growth (µm/day/cm²)
- Hair growth (µm/day/cm², mean median)
- TrichoScan Änagen/Telogen ratio
- Proportion of anagen hairs (%)
- Proportion of telogen hairs (%)
- Proportion of vellus hair (%)

To evaluate the safety based on:

- Any adverse events and adverse drug reactions reported
- Local tolerability assessments
- Vital signs and physical examination
- Abnormal safety laboratory parameters

Statistical methods:

Summary tables (descriptive statistics and/or frequency tables) will be provided for screening and/or baseline variables, efficacy variables, and safety variables. Continuous variables will be presented by descriptive statistics (n, mean, median, standard deviation, minimum, and maximum). Frequency counts and percentage of subjects within each category will be provided for categorical data. Summaries will be provided for each treatment dose, if applicable.

Descriptive summaries by study center will be presented for the primary efficacy endpoint.

Hypothesis

Since this is an exploratory trial no formal hypotheses are postulated. Comparisons by means of p-values will be interpreted in a descriptive manner.

Efficacy analysis:

Statistical analyses will be performed using two-sided tests and confidence intervals, as appropriate. The primary efficacy endpoint, the change from baseline for hair density on the scalp after 12 weeks, will be analysed using the exact Wilcoxon signed rank test to test versus zero. The secondary efficacy endpoints will be analysed using the same methodology as in the analysis of the primary efficacy endpoint.

Safety analysis:

All AEs reported during the trial period will be listed, documenting course, severity, investigator assessment of the relationship to the IP, and outcome. AEs will be coded using the MedDRA mapping system and tabulated by system organ class (SOC) and by preferred term. Listings of serious adverse events (SAE) and subjects who prematurely discontinued treatment due to AEs will be given.

Safety laboratory parameter (hematology, clinical chemistry) and vital signs will be

summarized descriptively, including changes from baseline. Urinalysis outcomes and outcomes of local tolerability assessments will be summarized by frequency counts.

Analysis populations:

Safety summaries will be performed on the safety analysis set. The Per-protocol set will be considered the primary efficacy subset of subjects. The Full analysis set will be used for a sensitivity analysis of the primary efficacy variable only.

1.1	Trial flow chart	

		Treatment period									
Visit number	Screening ^{a)}	1	2	3 - 21	22	23	24	25-36	37	38	EoT ⁱ⁾
Week	-3 to -1					1	- 12				
Day	-21 to -3	1	3	5 - 48	50	52	54	57 - 82	85	87	NA
Visit window (+/- days) with at least 1 day interval			1	1	1	1	1	1	1	1	1
Informed consent	X										
Physical examination ^{b)}	X	Х								Х	Х
Inclusion/exclusion criteria	X	Х									
Demographic data	X	X									
Medical and surgical history	X										
Vital signs °)	X	X								X	X
Concomitant medication	X	X	Χ	X	Х	X	X	X	X	X	X
Determ. of investing. Areas ^{d)}		Х									
Marking of test areas		Х									
Randomisation			Х								
Dot tattoo ^{e)}	X			X e)				X e)			
IP/ Placebo administration			X	х	Х		X	Х			
Shaving of treatment areas		Х				X				X	
TrichoScan		X f)	X			X f)	X		X f)	Х	
Safety assessment/ local tol.		X	Х	X	Х	X	X	X	X	X	Х
Blood sampling (haem. and clin chem) ^{g)}	X									X	X
Blood sampling (Hep B, Hep C, HIV)	X										
Urine sampling ^{h)}	X									X	X
Recording of AEs/SAEs		X	Χ	X	X	X	X	X	X	X	X

- a) The screening period is defined as the time between visit 0 and visit 1. The screening period will vary in length to accommodate flexibility in the planning of subject visit schedule.
- b) The physical examination will include: General appearance, mouth and throat, ears (left and right), lungs, abdomen, neurological
- c) Vital signs will include: Systolic and diastolic blood pressure (mmHg), heart rate (beats per minute), and body temperature
- d) The treatment areas will be evenly placed on the scalp
- e) The dot tattoo will be repeated if necessary during the course of the trial. Ensure that this performed at least 6 days prior to the next TrichoScan assessment.
- f) TrichoScan imaging will be performed without hair dye
- g) Haematology: haemoglobin, white blood cell count including differential cell count, red blood cell count, platelet count, coagulation (partial thromboplastin time and prothrombin time); Clinical Chemistry: Glucose, creatinine, total bilirubin, gamma-glutamyltransferase (GGT), alanine aminotransferase (ALAT), aspartate aminotransferase (ASAT), Electrolytes (Na, K), lactate dehydrogenase (LDH), C-reactive protein (CRP), total cholesterol
- h) Urine analysis (urine qualitatively): blood, ketones, glucose, protein, pH, nitrites, leucocytes, microscopy if results are positive for blood or protein
- i) End of Treatment (EoT) procedures should as far as possible be completed for all subject.

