12 STATISTICAL METHODS AND DETERMINATION OF SAMPLE SIZE

12.1 Statistical and Analytical Plans

Before unblinding the trial data, a separate statistical analysis plan (SAP), may be prepared.

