12.1.4 Summary Statistics

Data will be summarised by means of summary statistics. Continuous data will be presented with the number of observations, mean value, standard deviation, minimum median and maximum value. Categorical data will be presented as counts and percentages. The data will be presented for each dose level.

Descriptive summaries by study center will be presented for the primary efficacy endpoint only.

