12.1.5 Efficacy Analyses

The primary efficacy objective is to evaluate the hair density (No. of hairs per cm²) on the scalp after 12 weeks of treatment as compared to baseline. The relative change will be used, i.e. after 12 weeks of – Baseline

The hypothesis that the relative change from baseline is equal to zero will be analysed using the exact Wilcoxon signed rank test.

The secondary efficacy objectives will be analysed using the same methodology as in the analysis of the primary efficacy objective.

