12.1.11 Other Safety Assessments

Physical Examination

Physical examination will be presented in a shift table. The shift table will show the number of subjects who changed (compared to visit 1) from "normal" or "abnormal" at baseline to "normal" or "abnormal" at each time of assessment.

Vital Signs

Vital signs will be summarised by treatment combination, together with changes from baseline, by visit.

Laboratory Safety Assessments

For laboratory data, summary statistics will be produced for observed values and for changes from baseline to each visit. In addition, the number of abnormal and clinically significant observations will be tabulated for each treatment combination by visit. Abnormal values will be flagged in listings.

Shift tables will show the number of subjects who changed from below, within or above the reference range at baseline to below, within or above the reference range at each time of assessment.

For laboratory values which are below the limit of quantification, the value corresponding to the limit of quantification will be used when summarising data (e.g. if the result is <x.x then the value x.x will be used in the statistical analysis).

Local Tolerance Assessments

Local tolerance assessments will be summarised by dose administered to the respective treatment areas.

12.2 **Determination of Sample Size**

The change from baseline until end of the treatment period (delta) is the primary efficacy endpoint and the base for the sample size estimation.

The expected standard deviation for delta is 23.0 based on data published by Olsen EA et. al [12]. The expected change in hair density from baseline is 8 % which is 13.6 hairs/cm² assuming the baseline hair density is 170 hairs/cm².

Using a statistical power of 80 % and a two-sided significance level on 5 % the number of fully evaluable subject on the dose of interest is 23. Assuming a dropout rate of 10 % results in a need to include 26 subjects whom all are given the dose of interest.

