12.3 Justification for the sample size

12.3.1 Introduction

The assumptions for the design and power calculations are:

- The variable the powering is based on is Hair Density (HD, number of hair per cm²) and absolute change from baseline
- The hypotheses to be tested will be two-sided, i.e. no assumptions on the direction of the effect
- The estimation of the expected baseline hair density and expected standard deviation is based on the Olsen EA et. al [12]

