12.3.3 Sample size Formula

The following hypothesis is to be tested:

 $H_0: \mu = 0$ $H_1: \mu \neq 0$

Where μ is the expected value in the group (i.e. the mean in an infinite group) implying that μ is the expected absolute change over time within a certain dose level.

The following formula has been used to calculate the number of patients needed [13] (n=number of patients on the dose of interest):

$$n = \frac{\sigma^2 \times \left(\lambda_{\alpha} + \lambda_{\beta}\right)^2}{(\mu)^2}$$

In the formula above σ is the expected standard deviation, λ_{α} is the 1– α percentile of the standardized normal distribution and λ_{β} is the 1– β percentile of the standardized normal distribution. If the test is two-sided and the significance level is 0.0500 then λ_{α} = 1.9600. If the power is 80% then λ_{β} = 0.8416 and if the power is 90% then λ_{β} = 1.2816.

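### The only planned efficacy test compares change with zero; no dose is compared with placebo, so a change common to all treated areas could be read as a drug effect

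*Combined protocol and SAP*

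**What the plan says.** The synopsis (Statistical methods, Efficacy analysis) states that the primary endpoint, 12-week change in hair density, "will be analysed using the exact Wilcoxon signed rank test to test versus zero". Section 12.1.5 repeats this: "The hypothesis that the relative change from baseline is equal to zero will be analysed using the exact Wilcoxon signed rank test". It then extends it: "The secondary efficacy objectives will be analysed using the same methodology as in the analysis of the primary efficacy objective".

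The powering follows the same logic. In 12.3.3 the null hypothesis is μ = 0, with μ being "the expected absolute change over time within a certain dose level". Section 12.2 concludes that "the number of fully evaluable subject on the dose of interest is 23". Placebo enters neither the test nor the sample size.

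Otherwise, efficacy is only summarised descriptively. Section 12.1.4 says "The data will be presented for each dose level". Section 12.1.3 promises nominal p-values and confidence intervals but names no difference between treatments. Section 12.1 adds that "a separate statistical analysis plan (SAP), may be prepared".

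The design itself provides a control. Sections 7.1 and 9.6 give each subject two different treatments out of five, one per area, in a 5:5:5:5:4 ratio with placebo as the 4. Section 7.3 justifies the randomised, controlled, blinded design by its protection against bias.

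**The concern.** The primary objective is the efficacy of FOL-005. A before-after test within one dose cannot separate the drug from anything else that moves hair density over 12 weeks: repeated needling, shaving, season, or drift in imaging. Randomisation and placebo exist to remove such shared changes, but only if active and placebo areas are compared. As written, a shared rise could be reported as efficacy, and a shared fall could hide a real effect.

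The placebo row of the summary tables would show a shared change. Comparing rows or p-values by eye, however, gives no planned estimate of the difference and no measure of its uncertainty. It also ignores that the two areas on one scalp are paired.

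**Working it through.** **Inputs from the protocol.** SD of change 23.0, target change 13.6 hairs/cm² (8% of 170), two-sided 5%, power 80%, dropout 10% (12.2). Published SDs 19.7 on placebo and 22.5 on active (12.3.2). Allocation 5:5:5:5:4 over 120 areas (synopsis): 120 × 5/24 = 25 areas per active dose and 120 × 4/24 = 20 on placebo.

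**1. The plan's own figure.** n = σ²(λα + λβ)²/μ² = 23² × (1.9600 + 0.8416)² / 13.6² = 529 × 7.849 / 184.96 = 22.45, rounded up to 23. With dropout, 23/0.90 = 25.6, rounded up to 26. Both figures reproduce, but as a one-sample calculation with no placebo term.

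**2. The planned test when the drug does nothing.** Suppose all areas, placebo included, shift by the same amount. The shift sizes are assumptions. Simulating the exact two-sided signed rank test (normal changes, SD 23, n = 25, no dropout) gives, for one dose:

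| Shared rise (hairs/cm²) | 0 | 5 | 8 | 10 | 13.6 |
|---|---|---|---|---|---|
| Nominally significant | 4.8% | 16.9% | 36.6% | 52.6% | 78.8% |

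**3. Four doses together.** Assume 60 subjects with 5 per placebo-active pair and 6–7 per active-active pair, and within-subject correlation from 0 to 0.7.

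| Still no drug effect | No rise | 5-hair rise |
|---|---|---|
| At least one dose significant against zero | about 18% | 49–53% |
| At least one of four dose-placebo contrasts significant | about 15% | about 15% |

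Each dose-placebo contrast alone stays near 5%, because a shared shift cancels.

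Checking placebo's own test does not solve this. The pattern of at least one dose significant and placebo not significant occurs in 40–45% of trials at a 5-hair rise and 51–53% at 10.

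**4. Power of the comparison that is missing.** With independent areas, SE = 23 × √(1/25 + 1/20) = 6.90, and power for 13.6 is Φ(13.6/6.90 − 1.96) = Φ(0.01) = 50%. The difference detectable with 80% power is 2.8016 × 6.90 = 19.3 hairs/cm². After 10% loss (22.5 and 18 areas), SE = 7.27, power is 46%, and the detectable difference is 20.4.

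A model with a subject effect recovers power if the two areas on a scalp are correlated. The documents give no correlation, so a range is shown, using the pair layout of step 3:

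| Correlation | 0 | 0.3 | 0.5 | 0.7 |
|---|---|---|---|---|
| SE, SD 23 | 6.90 | 6.37 | 5.67 | 4.58 |
| Power | 50% | 57% | 67% | 84% |
| Power after 10% loss | 46% | 53% | 62% | 80% |

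With the published SDs and independent areas, SE = √(22.5²/25 + 19.7²/20) = √(20.25 + 19.40) = 6.30 and power is Φ(13.6/6.30 − 1.96) = 58%. At correlations 0.3, 0.5 and 0.7 it is 65%, 75% and 90%. After 10% loss the four values are about 54%, 60%, 70% and 87%.

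The documents do not fix the number of subjects per pair. With uneven placebo pairs (2, 4, 6 and 8 subjects), power at SD 23 before loss ranges over 55–58%, 64–69% and 81–87% for correlations 0.3, 0.5 and 0.7.

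**The case against.** The main reply is that the trial is declared exploratory: no formal hypotheses, descriptive p-values, no success rule tied to the test against zero, and room for a later SAP. That affects how firmly a p-value may be read. It does not change what is estimated, and an exploratory dose-finding trial still needs the effect relative to placebo. The SAP is optional, so nothing commits the sponsor to adding the contrast.

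Second, the by-dose means and SDs would let a reader work out an unpaired difference and a rough interval. This is true, and a shift present in all five rows would be visible. What is missing is a pre-specified estimate that uses the pairing.

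Third, the shared rises are assumed, and 13.6 makes the shared rise as large as the whole target effect. The simulation also uses absolute changes, while 12.1.5 speaks of relative change. The percentages therefore show a mechanism and do not predict this trial. With no shared shift, the two approaches have similar any-dose error, about 18% against 15%.

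Fourth, SD 23 is deliberately conservative. The published SDs raise the power of the contrast, as shown above, but 23 is the plan's own planning value.

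Three smaller points stand:

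- Testing by dose is explicit only in 12.3.3 and implied elsewhere. Any other grouping tested against zero would still lack a placebo comparison.
- Blinded central image reading protects against detection bias whichever test is used.
- The combination list in 9.6 prints the 0.025 and 0.050 µg pair twice and omits 0.050 with 0.100 µg, which 9.3 mentions. These passages must be reconciled. The effect on the power figures is under one percentage point.

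**Conclusion.** The concern holds and should be fixed before unblinding. The documents contain no estimate, interval or test of any dose against the 20 placebo areas, so the efficacy inference makes no use of the control the design provides. How often this would mislead depends on a shared change that the documents do not quantify: for a single inactive dose, about 5% with none, 17% at 5 hairs/cm² and 53% at 10 (normal changes, SD 23, 25 areas per dose).

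The stated 80% power does not carry over to the controlled question. At SD 23 and after 10% dropout, power for a 13.6 hairs/cm² difference is about 46–62% for correlations from 0 to 0.5 and about 80% at 0.7, given the assumed pair layout. The omission is certain from the text. The sizes are illustrations under stated assumptions.

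**What to change.** In 12.1.5 and the synopsis, make the primary analysis the difference from placebo for each dose, with 95% confidence interval and nominal p-value, using both areas of each subject. One suitable model takes 12-week absolute change in hairs/cm² as outcome, with treatment (five levels), that area's baseline density, side and centre as fixed terms and subject as a random effect. A rank-based paired method would also serve, and the covariates are a matter of choice. Keep the within-dose signed rank test as supportive, and apply the same contrast to the secondary endpoints.

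State in 12.1.5 whether change is absolute or relative, consistently with 12.3.1, which powers on "absolute change from baseline". In 12.2, say that the 80% power covers only the within-dose test against zero, and give the power of the dose-placebo contrast with its assumed SD, correlation and pair counts.

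The cost is protocol or SAP wording and one further analysis of data already collected. Randomisation and visits are unchanged. The drawback is that the stated power for the controlled comparison will, under most of the assumptions above, be below 80%. Reporting the contrast as an estimate with its interval suits an exploratory trial and does not by itself require more subjects.
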